## 7.6 Test Article Administration

### 7.6.1 Intravenous Treatment Phase

The iv-treatment phase (minimum 2 days) will follow a double-blind, double-dummy design for omadacycline and moxifloxacin. Infusions of 100 mg omadacycline or matched placebo will be administered continuously, without interruptions, over 30 minutes ( $\pm$  5 minutes). On Day 1, if QD dosing is selected, the 200 mg infusion of omadacycline or matched placebo will be administered continuously, without interruptions, over 60 minutes ( $\pm$  5 minutes). On Day 1 of iv treatment, if twice a day dosing (BID) was selected, subjects on the moxifloxacin treatment arm will receive an additional placebo infusion to match the t = 12 h infusion. Infusions of moxifloxacin or matched placebo will be administered continuously, without interruptions, over 60 minutes ( $\pm$  5 minutes).

The first dose of test article should be administered within 4 hours of randomization. All infusion start and stop times are to be recorded in the source documents and on the eCRF. Because the color of the test article and placebo infusions are different, all infusion bags and iv tubing will be covered with materials provided by the sponsor (as described in the Pharmacy Manual) so that

subjects and blinded study personnel will not know the identity of the test article being administered. Subjects in each study arm will receive the same infusion volumes with the same blinded administration instructions. All iv infusions will be administered by qualified blinded personnel. However, unblinded personnel may administer the iv infusions provided they will not be performing any efficacy assessments. If gravity administration is not the standard of care, then an infusion pump may be used. If an infusion pump is used, then an unblinded administrator will be required. Subjects may receive iv treatment in certain outpatient centers in circumstances where the principal site investigator has identified that sufficient resources are available to complete all study procedures as defined in the protocol and the sponsor or sponsor's designee has reviewed and approved the process for outpatient iv test article administration.

Please refer to Table 1 for more detail on the Treatment regimens for iv dosing.

Infusion Timepoint a	Infusion Number	Omadacycline Arm b,c	Moxifloxacin Arm b,c
	1	omadacycline 100 mg in 100 mL NS	100 mL NS placebo

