# **9 STUDY ACTIVITIES**

#### 9.1 Screening Phase

The Screening visit should be completed within a 24-hour period prior to randomization. The Screening procedures will be used to establish subject eligibility and baseline characteristics for each subject. Following the signing of an ICF, the site staff will collect/perform the assessments detailed in Appendix 1.

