## **12.3** Analysis Populations

The following subject analysis populations have been defined for the various analyses of efficacy and safety:

- The ITT population will consist of all randomized subjects.
- The micro-ITT population will consist of subjects in the ITT population who have at least 1 causative pathogen identified at Screening from culture of a respiratory specimen (eg, respiratory fluid obtained by bronchoalveolar lavage or bronchoscopy; pleural fluid obtained by thoracentesis; or expectorated or induced sputum meeting adequacy criteria), culture of blood, or from a culture-independent method (eg, positive urinary antigen test for *Streptococcus pneumoniae* or *Legionella pneumophila*, or positive serology for *Legionella pneumophila*, *Mycoplasma pneumoniae* or *Chlamidophila pneumoniae*).
- The CE population will consist of all ITT subjects who received test article, have a qualifying CABP, an assessment of outcome, and meet all other evaluability criteria detailed in the SAP.
- The microbiologically evaluable (ME) population will include subjects in the CE population who have at least 1 causative pathogen identified at Screening.
- The Safety population will consist of all randomized subjects who receive test article.

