6.1.3 Microbiological Intent-to-Treat (microITT) Population

The microITT population will consist of all subjects in the ITT population who have at least one causative bacterial pathogen identified from a culture of a respiratory specimen (eg, respiratory fluid obtained by bronchoalveolar lavage [BAL] or bronchoscopy; pleural fluid obtained by thoracentesis; or expectorated or induced sputum meeting adequacy criteria as defined by the Gram stain results), culture of blood or from a culture-independent method (eg, positive urinary antigen test for *Streptococcus pneumoniae* or *Legionella pneumophila*, or positive serology for *Legionella pneumophila*, *Mycoplasma pneumoniae*, or *Chlamydophila pneumoniae*) at baseline.

Pathogen determination of typical bacteria is based on the genus and species identification from the central laboratory. If the local laboratory grows an acceptable pathogen but the central laboratory is not able to grow the isolate, if isolates are lost during transportation or storage, or there are major discrepancies between the local and central laboratory in the identification of species, the central laboratory or other Sponsor designee will request that the local laboratory resend the isolate. If the central laboratory cannot determine the genus and species of the isolate for any reason, the local laboratory determination of genus and species will be used for pathogen identification. The central laboratory identification of genus and species is used for analysis unless no central determination exists in which case the local laboratory determination is used.

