In general, baseline is defined as the 24-hour period prior to the administration of the first dose of test article. However, if the subject is unable to produce a sputum sample at baseline or the sputum sample is not adequate based on the Gram stain criteria, a specimen obtained within 24 hours after the first dose of test article may be considered a baseline sample. If the sputum sample collected in the 24-hour period prior to the administration of the first dose of test article is not adequate based on the Gram stain criteria and the sputum sample obtained within 24 hours after the first dose of test article is not adequate based on the Gram stain criteria and the sputum sample obtained within 24 hours after the first dose of test article is not adequate based on the Gram stain criteria and the sputum sample obtained within 24 hours after the first dose of test article is not adequate based on the Gram stain criteria and the sputum sample obtained within 24 hours after the first dose of test article is not adequate based on the Gram stain criteria, only the sputum sample collected in the 24-hour period prior to administration of the first dose of test article will be considered baseline. UAT samples up through 24 hours after the first dose of test article may be considered the baseline sample, if a previous sample was

not taken or was found to be negative. Blood samples up through 24 hours after the first dose of test article may be considered the baseline sample, if a previous sample was not taken or was found not to have a pathogen.

The following isolates will always be considered a pathogen:

Streptococcus pneumoniae

- Positive BAL, bronchoscopy, pleural fluid, or blood culture; or
- Positive sputum culture in the presence of an adequate Gram stain defined as having > 25 polymorphonuclear neutrophils (PMNs)/Low Power Field (LPF) and < 10 Squamous Epithelial Cells (SECs)/LPF; or
- Positive urinary antigen test

Haemophilus influenzae

- Positive BAL, bronchoscopy, pleural fluid, or blood culture; or
- Positive sputum culture in the presence of an adequate Gram stain (> 25 PMNs/LPF and < 10 SECs/LPF)

Staphylococcus aureus

- Positive BAL, bronchoscopy, pleural fluid, or blood culture
- Positive sputum culture in the presence of an adequate Gram stain (> 25 PMNs/LPF and < 10 SECs/LPF)

Moraxella catarrhalis

- Positive BAL, bronchoscopy, pleural fluid, or blood culture; or

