- Positive sputum culture in the presence of an adequate Gram stain (>25 PMNs/LPF and < 10 SECs/LPF)

Legionella pneumophila

- Positive BAL, bronchoscopy, pleural fluid, or blood culture; or
- Positive sputum culture, regardless of Gram stain findings; or
- Positive or borderline acute (baseline) or positive or borderline convalescent (PTE) IgM (Euroimmun IgM ELISA IgM ≥0.80 ratio).
- Negative acute (baseline) and positive or borderline convalescent (PTE) IgG (Euroimmun IgG ELISA IgG ≥16 RE/mL).
- A positive urine antigen test

Mycoplasma pneumoniae

- Positive or borderline acute (Baseline) or positive or borderline convalescent (PTE) IgM (Euroimmun IgM ELISA IgM ≥0.80 ratio).
- Negative acute (Baseline) and positive or borderline convalescent (PTE) IgG (Euroimmun IgG ELISA IgG ≥16 RE/mL).

Chlamydophila pneumoniae

- Positive or borderline acute (Baseline) or positive or borderline convalescent (PTE) IgM (Euroimmun IgM ELISA IgM ≥0.80 ratio)
- Negative acute (Baseline) and positive or borderline convalescent (PTE) IgG (Euroimmun IgG ELISA IgG ≥16 RE/mL)

The following isolates are considered as contaminants from respiratory specimens rather than pathogens of CABP: *Candida* spp. and other fungi, *Enterococcus* spp., viridans streptococci, coagulase-negative staphylococci, *Micrococcus* spp., *Neisseria* spp. other than *N. meningitidis*, *Corynebacterium* spp. and other coryneforms, *Lactobacillus* spp., *Vibrio* spp., *Capnocytophaga* spp., *Cardiobacterium* spp., *Flavobacterium* spp, *Staphylococcus lugdunensis*, *Staphylococcus capitis*, *Staphylococcus capiter*, *Staphylococcus haemolyticus*, *Staphylococcus haemolyticus*, *Staphylococcus simulans*, *Streptococcus saprophyticus*, *Staphylococcus sciuri*, *Staphylococcus simulans*, *Streptococcus epidermidis*, *Streptococcus viridans*, *Staphylococcus warneri*, *Staphylococcus xylosus*

Other isolates identified from culture of blood and respiratory specimens will be reviewed in a blinded manner by the Sponsor on a case-by-case basis for determination of whether the organism is a pathogen for CABP.

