 - Subjects will be defined as an Indeterminate if the investigator cannot determine whether the subject is a Clinical Success or Failure at the EOT or PTE Visits or the subject has a missing response Table 4. By definition, subjects with an Indeterminate response are included in the denominator for analyses in the ITT and microITT populations, and thus, are considered Clinical Failures. Subjects with an

Indeterminate response are excluded from the CE-EOT, CE-PTE, ME-EOT and ME-PTE populations.

- For microbiologic response:
 - If no post-baseline source specimen is obtained and the subject has an investigator's assessment of Clinical Response, the per-pathogen microbiological response is based on the investigator's assessment of Clinical Response (ie, the response is a presumed response). A per-pathogen microbiological response at the EOT Visit or PTE Visit will be considered Indeterminate only if the Clinical Response at EOT or PTE is also Indeterminate.
- Missing values for other individual data points will remain as missing. Missing values will not be imputed and only observed values will be used in data analyses and presentations.
- Where individual data points are missing, categorical data will be summarized based on reduced denominators (ie, only subjects with available data will be included in the denominators).

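### Micro-ITT is labelled as a baseline population but admits atypical pathogens found only in PTE serum, which selects on PTE attendance; the SAP's specimen window is also narrower than the protocol's for respiratory and urine samples

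*SAP*

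**What the plan says.** **Who is in micro-ITT.** Protocol 12.3 takes ITT subjects who "have at least 1 causative pathogen identified at Screening from culture of a respiratory specimen", or from blood culture or a culture-independent method, with positive serology among the examples. SAP 6.1.3 requires "at least one causative bacterial pathogen identified from a culture of a respiratory specimen" or one of the same other routes, and its sentence closes with the words *at baseline*.

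**What then counts as a pathogen.** The organism list in SAP 6.1.3 accepts *Legionella pneumophila*, *Mycoplasma pneumoniae* and *Chlamydophila pneumoniae* on a positive or borderline IgM at either baseline or PTE, or on "Negative acute (baseline) and positive or borderline convalescent (PTE) IgG". Protocol 8.14.3 draws serology blood at Screening and PTE only.

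**Missing outcomes.** SAP 7.3 says that "subjects with an Indeterminate response are included in the denominator for analyses in the ITT and microITT populations", so they count as failures.

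**Specimen window.** SAP 6.1.3: "In general, baseline is defined as the 24-hour period prior to the administration of the first dose of test article". SAP 7.2 glosses the same 24 hours as Day -1 or 1, and SAP Table 8 places Screening assessments within 24 hours before first dose. Protocol 9.1 runs the clock from randomisation: "The Screening visit should be completed within a 24-hour period prior to randomization". Protocol 7.6.1 adds: "The first dose of test article should be administered within 4 hours of randomization". SAP Appendix 1, footnote b, also counts Screening from randomisation. Protocol 8.14.1 asks only that Screening respiratory specimens precede the first dose. Protocol 8.12.2.2 limits blood cultures to 24 hours before first dose.

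**The concern.** Clinical response by causative pathogen is a stated secondary objective. A subject whose only evidence of an atypical pathogen is PTE serum must have survived, attended PTE and given blood. Attendance is a post-randomisation event tied to outcome. A comparable subject who died, withdrew or was lost before PTE is never recognised as having the pathogen, so the SAP 7.3 rule that counts missing outcomes as failures cannot reach that subject.

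The selection carries further:

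- **ME-PTE.** SAP 6.1.4.5 keeps EOT failures, and deaths between EOT and PTE, as evaluable failures without a PTE visit. SAP 6.1.5 also requires micro-ITT membership for ME-PTE, so such a failure drops out of ME-PTE unless another test was positive.
- **Microbiological response.** Under SAP 5.2.2.3, atypicals known only from serology can have only a presumed or indeterminate response. A raised clinical rate therefore passes into the microbiological tables.
- **Visibility.** SAP 8.2.1 tabulates by testing modality only for *S. pneumoniae* and *L. pneumophila*. No planned table separates acute from convalescent serology.

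The window is a second, smaller matter. Micro-ITT membership is assigned programmatically (SAP 6.2.2), so the programmer needs one rule, and the documents give two.

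**Working it through.** **Plan's own figure.** Expected micro-ITT size: 0.30 × 670 = 201, as stated in Protocol 12.2 and SAP 5.1.1.

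**1. Effect of entry through PTE serum**

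Input from the documents: PTE success p = 85% (ITT assumption, SAP 5.1.1).

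Assumptions, because the documents give neither figure:
- a = share not attending PTE, 3 to 10%.
- s = share of the true micro-ITT identifiable only from PTE serum, 10 to 40%.
- All non-attenders are non-successes.

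As a guide to the top of the range for a, CABP-1200 lost 329 − 295 = 34 of 329 (10.3%) and 331 − 296 = 35 of 331 (10.6%) between ITT and CE, for all reasons together. So 10% is a high value for PTE non-attendance alone.

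Observed success among PTE-serology-only subjects = p/(1 − a). Observed success in the whole micro-ITT = p/(1 − s·a). Subjects removed = 201·s·a.

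| a | PTE-serology-only success | Rise in whole micro-ITT, s = 10% / 40% | Subjects removed, s = 10% / 40% |
|---|---|---|---|
| 3% | 85/0.97 = 87.6% | 0.3 / 1.0 points | 0.6 / 2.4 |
| 5% | 85/0.95 = 89.5% | 0.4 / 1.7 points | 1.0 / 4.0 |
| 10% | 85/0.90 = 94.4% | 0.9 / 3.5 points | 2.0 / 8.0 |

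Between arms: with equal a and s, both arms shift alike and the spurious difference is zero. With a = 3% in one arm and 8% in the other, it is 85/(1 − 0.008) − 85/(1 − 0.003) = 0.4 points at s = 10%, and 85/(1 − 0.032) − 85/(1 − 0.012) = 1.8 points at s = 40%. It favours the arm with more loss. For scale, the 95% half-width for a difference with 201 subjects split equally is 1.96 × √(2 × 0.85 × 0.15/100.5) = 9.9 points.

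The same selection applies to ECR in micro-ITT, but the documents do not support a figure for it.

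**2. Specimen window**

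Oldest compliant Screening respiratory or urine specimen at first dose: 24 + 4 = 28 hours. SAP limit: 24 hours. Gap: up to 4 hours.

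Example: urine taken 23 hours before randomisation, with dosing 3 hours after it, is 26 hours old. It complies with the protocol but lies outside the SAP's 24 hours. If dosing is at 10:00 on Day 1, the sample was taken at 08:00 on Day -1, so SAP 7.2's two descriptions disagree about it. If that antigen test was positive, SAP 6.1.3's later-sample exception does not help, because it applies only when the earlier sample was absent or negative.

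If collection is uniform over the 24 hours before randomisation (assumption) and the dose follows after d hours, a share d/24 is older than 24 hours at dosing: 0.5/24 = 2.1% to 4/24 = 16.7%. The documents do not say how many of the 201 rest only on such a specimen. If it were a quarter, 201 × 0.25 × d/24 gives 1 to 8 subjects; if half, 2 to 17.

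Blood cultures have no gap, since protocol and SAP use the same clock.

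**The case against.** The other side has good points.

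- **Convalescent serology is planned and disclosed.** The protocol collects it and names serology as a route into micro-ITT, and SAP 5.2.2.3 refers openly to acute and convalescent serology. It is a late read-out of an infection present at baseline. This stands: the method is legitimate and need not leave the main rows.
- **The rows are pooled.** SAP 9.3 tabulates each pathogen across all routes. Subjects with positive acute IgM, or with *Legionella* by culture or urine antigen, stay in the same row if they miss PTE and then count as non-success. This stands, and dilutes the effect.
- **Failures can enter.** Protocol 8.24 and 9.4.1 ask subjects who discontinue or withdraw early to attend PTE, and SAP Table 4 carries EOT failures forward. This limits non-attendance but does not restore those who never gave PTE blood.
- **Culture and antigen results are not fixed strictly before dosing either.** SAP 6.1.3 accepts sputum, urine antigen and blood up to 24 hours after first dose. True, but the SAP writes these down as exceptions; PTE serology is not so described.
- **The window rule is softened** by its opening words and by the Day -1 or 1 gloss. This makes the exclusion ambiguous, not certain. The exceptions still extend only forward in time.
- **Stakes are modest.** The by-pathogen results are descriptive, isolate review is blinded, and a listing will show specimen type and modality. All true. A listing does not, however, give rates without the selected subjects.

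**Conclusion.** The point holds in two parts.

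First, the baseline label and the PTE-serology route conflict, and entry by that route depends on attending PTE. Pre-PTE deaths and losses with no other positive test are removed instead of counted as non-successes, which tends to raise within-arm success for atypical pathogens in micro-ITT and ME-PTE. The size cannot be derived from the documents. Under the stated assumptions it is about 0.3 to 3.5 points across micro-ITT.

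Second, the SAP window is narrower than the protocol's Screening window for respiratory and urine specimens, and disagrees with the SAP's own Appendix 1. Read literally, a positive compliant specimen taken 24 to 28 hours before dosing is not baseline.

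Stronger readings that a reader might infer, and why they are not supported:

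- *By-pathogen success is inflated by about 3 to 9 points.* That range (87.6 − 85 = 2.6 to 94.4 − 85 = 9.4) belongs to PTE-serology-only subjects, and the plan has no such row.
- *The treatment comparison is biased.* Only if attendance differs by arm, and nothing in the documents says that it will.
- *Micro-ITT shrinks.* PTE serology adds subjects and the window may remove some; the net effect is not shown.
- *The specimen share applies to all 201.* That would count blood cultures, which have no gap, and diagnoses made only from PTE serum.

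The affected analyses are secondary and descriptive. The primary ITT analysis of ECR and the sample size of 670 are unaffected.

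**What to change.** 1. **Serology.** In SAP 6.1.3, state PTE serology as an explicit exception to the baseline requirement. In SAP 9.3 and 9.4, keep the main tables and repeat the micro-ITT and ME-PTE results, overall and by pathogen, clinical and microbiological, without subjects identified only by PTE serology. Show those subjects as a separate row, footnoted as conditional on attending PTE.
2. **Window.** In SAP 6.1.3, 7.2 and Table 8, set the pathogen-baseline window for respiratory and urine specimens to run from 24 hours before randomisation to first dose, with the existing post-dose exceptions kept. Leave blood cultures at 24 hours before first dose, as in Protocol 8.12.2.2; moving them too would create a new mismatch.

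Cost: SAP wording and one extra table split, from data already collected. Atypical-pathogen counts will be smaller in the sensitivity analysis. A routine pre-consent respiratory specimen older than 24 hours at randomisation would still fall outside the window.

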6.1.4 Clinically Evaluable (CE) Populations

Two CE populations will be defined: the CE-EOT and the CE-PTE. Subjects will be *included* in or *excluded* from the CE analysis sets based on the criteria listed below.

6.1.4.1 Diagnosis of CABP

To be included in the CE-EOT and CE-PTE populations, subjects must meet the following protocol defined inclusion criteria that describe the CABP:

Inclusion Criterion 3: Has at least 3 of the following symptoms:

- Cough
- Production of purulent sputum
- Dyspnea (shortness of breath)
- Pleuritic chest pain.

Inclusion Criterion 4: Has at least 2 of the following abnormal vital signs:

- Fever or hypothermia documented by the investigator (po or rectal temperature > 38.0°C [100.4°F] or < 36.0°C [95.5°F])
- Hypotension with systolic blood pressure (SBP) < 90 mmHg
- Heart rate > 90 bpm
- Respiratory rate (RR) > 20 breaths/minute.

Inclusion Criterion 5: Has at least 1 clinical sign or laboratory finding associated with CABP:

- Hypoxemia Partial pressure of arterial oxygen (PaO₂) < 60 mmHg by arterial blood gas (ABG)
- Physical examination findings of pulmonary consolidation (dullness on percussion, bronchial breath sounds, egophony, rales, rhonchi, or decreased breath sounds)
- An elevated total white blood cell (WBC) count (> 12,000 cells/mm³) *or* leucopenia (WBC < 4,000 cells/mm³) *or* elevated immature neutrophils (> 15% band forms regardless of total peripheral WBC count).

Inclusion Criterion 6: Has disease categorized as being PORT III or IV at Screening

Inclusion Criterion 7: Radiographically-confirmed pneumonia, ie, new or progressive pulmonary infiltrate(s) on chest X-ray (CXR) or chest computed tomography (CT) scan consistent with acute bacterial pneumonia within 48 hours prior to the first dose of test article.

The Sponsor Medical Monitor will also review those subjects with a concomitant illness identified after baseline that could have presented at baseline as pneumonia, including COVID-19. If it is determined that the subject does not have pneumonia but had another condition such as lung cancer or COVID-19 at baseline, the subject will not be evaluable for the CE populations. Any subject who is confirmed or suspected to have severe acute respiratory syndrome coronavirus 2 (SARS-CoV-2) infection based on local standard-of-care assessments during the post-randomization period may be excluded from the CE populations based on Sponsor review.

6.1.4.2 **Prior Antibiotic Therapy**

Subjects will be excluded from the CE populations if they meet the prior antibiotic exclusion criteria:

Exclusion Criterion 1: Has received 1 or more dose(s) of a potentially effective systemic antibacterial treatment within the 72 hours prior to the first dose of test article (a subject will be considered to have received a potentially effective systemic antibacterial treatment if the pathogen identified as causing infection is shown to be susceptible to the antibacterial given or, in the circumstance where a pathogen is not identified, if the antibacterial agent is approved for treatment of pneumonia or is known to have activity against any of the leading

causes of CABP [eg, *Streptococcus pneumoniae, Haemophilus influenzae, Moraxella catarrhalis, Staphylococcus aureus, Legionella pneumophila*]). EXCEPTION: Subjects (not exceeding 25% of the total study population) may be eligible despite prior antibacterial therapy if they have been treated with a single dose of a short-acting antibacterial (ie, an antibacterial whose standard dosing regimen is more frequent than once per day, see Appendix 4 of the protocol).

